**Pregnancy Test**

Female subjects of childbearing potential will have a pregnancy test (serum or urine) before exposure to research-related radiation. A woman who is pregnant may not participate in this study and must tell us if she may have become pregnant during the previous 14 days because the pregnancy test is unreliable during this time. If a false positive pregnancy test is suspected, e.g., perimenopausal condition, an obstetrician will be consulted to determine if she is/is capable of becoming pregnant.

**Ga-DOTATOC PET/CT Scan**

Study participants who complete Visit 1 and have been deemed eligible, will undergo the Ga-DOTATOC PET/CT. Subjects may be offered a medication (alprazolam or lorazepam) to help them relax. The injected dose for adults will be 3-4 mCi (target: 4 mCi +/- 10%) containing <50 µg Ga-DOTATOC and will be injected via IV access lines (peripheral or central lines are acceptable.). The dose for children will be 0.043 mCi/kg with a maximum dose of 3 mCi. A low tube current CT will be obtained for attenuation correction and localization of PET/CT data. If a diagnostic CT scan is also clinically indicated, this can be performed on the PET/CT system in the same imaging session. All investigational PET/CT scans will be read by a board-certified nuclear medicine physician with established expertise. A report will be generated for the site(s) of the primary tumor (if visible/present) and metastases, which will be entered into the patient's medical record. If contrast-enhanced CT scans are obtained, these will be interpreted by the subspecialty radiologist per clinical routine and entered into the chart.

**Investigational Radiopharmaceutical Administration**

Ga-DOTATOC will be administered intravenously in conjunction with the PET/CT scan. The one-time nominal injected dose will be 4mCi (+/- 10%) containing <50 µg Ga-DOTATOC (estimated, allowing for adherence of peptide to glassware or syringes, a portion of the 50 µg original quantity used for QC, etc). The pediatric dose will be 0.043 mCi/kg with a minimum dose of 0.3 mCi and a maximum dose of 3 mCi in children <18 years old.

Ga-DOTATOC is produced at the University of Iowa PET Imaging Center by qualified personnel following USP <823> standards. All quality control tests will be completed satisfactorily prior to final release of the drug product, with the exception of sterility testing (test takes two weeks for completion). Subjects will be observed and monitored in the PET/CT area until the scan is completed which is approximately for 90 min after the administration of Ga-DOTATOC (60 min uptake period before imaging starts and approximately 30 min imaging time). The subject or his/her guardian will be queried for constitutional symptoms suggesting an adverse reaction to the investigational radiopharmaceutical. These will be evaluated as a drug-related adverse reaction. Staff will release subjects from clinic as appropriate, based on query results. The following day, all subjects will be contacted by phone or seen in the clinic and again asked if untoward/adverse events occurred after release. Any observed adverse events will, of course, be treated immediately and appropriately, and reported to the University of Iowa IRB and the FDA in accordance with established guidelines.

**Data Analysis:**

The primary end-point of the study is the change in management of patients based on findings of the Ga-DOTATOC PET/CT scan. UIHC referring physicians will be asked to fill out pre-PET and post-PET scan forms (Appendix II) to provide information on the management and treatment strategy of the patient before the Ga-DOTATOC PET/CT and after the information from the Ga-DOTATOC PET/CT study is available. This is the same methodology used in the National Oncologic PET Registry study; change in management strategy criteria are modified for the specific treatment strategies used in NET (Table 2).

Table 2: Criteria for minor change, major change and no change in management strategies based on comparison of pre-PET and post-PET plans.

Post-PET plan	Pre-PET plan									
	Watch	More Imaging	Octreotide LAR / Lanreotide	Tissue biopsy	Primary Debulking Surgery	PRRT	Chemotherapy OR Other Biological Modifiers	Liver Directed Therapy 	External beam radiotherapy	Supportive care
Watch	No change	Minor	Major	Minor	Major	Major	Major	Major	Major	Minor
More imaging	Minor	No change	Major	Minor	Major	Major	Major	Major	Major	Minor
Octreotide LAR / Lanreotide	Major	Major	No Change	Major	Major	Major	Major	Major	Major	Major
Tissue biopsy	Major	Major	Major	No change	Major	Major	Major	Major	Major	Major
Primary Debulking Surgery	Major	Major	Major	Major	No change	Major	Major	Major	Major	Major
PRRT 	Major	Major	Major	Major	Major	No change	Major	Major	Major	Major
Chemotherapy or Other Biological Modifiers 	Major	Major	Major	Major	Major	Major	No Change	Major	Major	
Liver Directed Therapy 	Major	Major	Major	Major	Major	Major	Major	No change	Major	Major
External beam radiotherapy	Major	Major	Major	Major	Major	Major	Major	Major	No change	Major
Supportive care	Minor	Minor	Major	Major	Major	Major	Major	Major	Major	No change

1: mTOR inhibitors, tyrosine kinase inhibitors  
2: Radiospheres, chemembolization, liver transplant  
3: Peptide Receptor Radionuclide Therapy

Subjects whose post-scan treatment plan represents a major change (whether or not the pre-scan treatment plan was a major change), will be presented at the Neuroendocrine Tumor Board, for a consensus recommendation regarding treatment. The minutes of this tumor board discussion and recommendation will be retained with the subject's study chart.

## Risks

### Risks of Study Drug

Research radiation dose estimate: Our calculations estimate that the effective whole-body dose of the Ga-DOTATOC PET/CT is approximately 1.6 rem, less than the radiation dose from a conventional F-FDG PET/CT scan of about 2.4 rem, assuming the standard use of a "low-dose" CT for anatomic localization and attenuation correction, as described in our proposed imaging protocol. The U.S. national annual background dose for humans is approximately 0.36 rem. The maximum annual permissible whole body radiation dose to a career radiation worker (e.g., a radiologist, nuclear medicine technologist, etc.) is 5.0 rem. Thus, the one-time dose to the patient for the investigational PET/CT will be approximately one-third of the annual permissible dose to a career radiation worker and about 5 years' worth of background radiation in the US. The increased risk to the patient, who will have a known current life-threatening malignancy, for a second radiation-induced malignancy from this investigational radiation exposure is extremely low (estimated < 1%). Given the risk of death from either delay in diagnosis or under-treatment of these known malignancies, we feel the added radiation burden to the patient is well within the patient's best interest if Ga-DOTATOC PET/CT imaging adds value.

### Risks of Study Procedures

Risks of Investigational PET/CT: An adverse reaction to the investigational radiopharmaceutical is possible though not reported. Additional risks include radiation exposure from the investigational PET/CT

scan, dosage infiltration, risks from IV access, and the inconvenience of the investigational PET/CT scan. If a subject elects to take medication to help them relax for the scan, they may experience drowsiness or unclear thinking. They will be instructed not to drive or operate machinery for 12-24 hours after receiving the medication. A driver will be required, if this type of medication is given the day of the scan.

Children may require sedation or anesthesia to remain still during the PET scanning procedure. The risks of sedation include a reaction to the medication used for sedation or anesthesia. If anesthesia is required, there is a risk of injury to the throat or airways from insertion of the breathing tube.

## **Reporting Adverse Events or Unanticipated Problems Involving Risk to Subjects or Others**

### **Adverse Event Terminology**

#### **Adverse Event**

1. An AE is "any untoward medical occurrence in a patient or clinical investigation subject administered a pharmaceutical product and which does not necessarily have a causal relationship with this treatment". An adverse event can therefore be any unfavorable and unintended sign (including an abnormal laboratory finding), symptom, or disease temporally associated with the use of a medicinal (investigational) product, whether or not considered related to the medicinal (investigational) product. AEs include any of the following:

- Subject deterioration due to the primary illness at the onset of the trial
- Intercurrent illnesses
- Drug interactions
- Events related or possibly related to concomitant medications
- Abnormal laboratory values or changes of vital signs, as well as significant shifts from baseline within the range of normal, considered to be clinically significant by the Investigator.

#### **2. Adverse Drug Reaction**

In the pre-approval clinical experience with a new medicinal product or its new usage, particularly as the therapeutic dose(s) may not be established, an adverse drug reaction is defined as:

*All noxious and unintended responses to a medicinal product related to any dose should be considered adverse drug reactions (ADR).*

#### **3. Unexpected Adverse Drug Reaction**

An unexpected ADR is:

- *An adverse drug reaction, the nature or severity of which is not consistent with the applicable product information, also known as reference safety information.*

#### **4. Serious Adverse Event/Serious Adverse Drug Experience**

During clinical investigations, serious AEs may occur. If the event is suspected to be drug-related, the event may be significant enough to lead to important changes in the way the medicinal product is developed (e.g. change in dose, population, needed monitoring, consent forms). This is particularly true for reactions, which, in their most severe forms, threaten life or function. A serious AE (SAE) or serious adverse drug experience (SADE) is any untoward medical occurrence that:

- Results in death.
- Is life-threatening. "Life-threatening" refers to an event in which the subject is at risk of death at the time of the event; it does not refer to an event which hypothetically might have caused death if it were more severe (ICHE6).
- Requires inpatient hospitalization or prolongation of existing hospitalization.
- Results in persistent or significant disability/ incapacity (as per reporter's opinion).
- Is a congenital anomaly/birth defect.
- Is another medically important condition. Important medical conditions that may not result in death, be life-threatening or require hospitalization may be considered as SAEs or SADEs when, based upon appropriate medical judgment, they may jeopardize the subject or may require intervention to prevent one of the outcomes listed in the definition above. Examples of such events are

intensive treatment in an emergency room or at home for allergic bronchospasm; blood dyscrasias or convulsions that do not result in hospitalization; or development of drug dependency or drug abuse.

- [Code of Federal Regulations Title 21, Volume 5, 21CFR312.32, revised April 1, 2006].
- Please note: Serious is not synonymous with severe. An event may be severe (e.g., severe headache) but still be of minor medical significance. Serious refers to an event that poses a threat to the subject's life or functioning.

## **5. Assigning Severity to an Adverse Event**

Severity of adverse events will be graded according to NCI Common Terminology Criteria for Adverse Events version 4.0 (CTCAE v4.0) which is available at <http://ctep.cancer.gov/reporting//ctc.html>.

## **6. Assigning Relationship of Adverse Event to Study Drug (Causality)**

The Investigator will determine the relationship of each adverse event. Descriptions of the three classification categories are as follows:

### **Not Related**

Exposure to study drug has not occurred; administration of study drug and the adverse event are not reasonably related in time; or the AE is considered by the Investigator to be due to a pre-existing condition, a known manifestation of the target disease, a recurrent condition, or is likely explained by environmental or diagnostic therapeutic factors or was preexisting and did not deteriorate.

### **Possibly Related**

The AE occurred during or within a reasonable period of time after administration of the study drug, or a pre-existing event worsened within an appropriate period of time after administration of study drug, but the AE could be explained equally well by factors or causes other than exposure to the study drug. This category will also be used if there is a lack of information, or insufficient or conflicting evidence exists for classifying the causality of the AE.

### **Probably Related**

The AE occurred during or within a reasonable period of time after administration of the study drug or a pre-existing event worsened within an appropriate period of time after administration of study drug, and at least one of the following criteria is applicable:

- the event could not be explained by the clinical condition or history of the subject, environmental or toxic factors, or other diagnostic or therapeutic measures;
- the event was an expected ADR associated with study treatment or a class-labeled drug effect;
- the AE subsided or disappeared after withdrawal or dose reduction of study treatment; or
- the AE recurred after re-exposure to study treatment.

## **Adverse Event Recording and Reporting**

### **1. Adverse Event Recording**

At baseline, all SAEs and study-related AEs since signing of the Informed Consent Form will be recorded. After initial study drug administration, all AEs will be recorded. Each AE occurring to a subject, either spontaneously revealed by the subject or observed by the Investigator, whether believed by the Investigator to be related or unrelated to the study drug, must be recorded on the AE Case Report Form and on the subject's file. Subjects will report the type and severity of AEs without being given a list of fixed symptoms beforehand. The Investigator will determine the relationship of any AE to study drug (causality) and record it on the appropriate section of the AE CRF as well as the start date of the event, event grade, and whether or not the event meets one or more of the definitions of an SAE. Clinically significant changes in vital signs (e.g., tachycardia) or other clinically significant changes observed by the physician will be entered in the appropriate CRF.

## 2. Serious Adverse Event Reporting

All SAEs must be reported promptly to the PI and will follow IRB and IND regulatory reporting requirements. SAEs should be followed to resolution or stabilization, even if this is after the study reporting period.

### Data and Safety Monitoring

**See Appendix 1 for Data and Safety Monitoring Plan**

### Assessing Toxicity:

Toxicity will be graded according to NCI's Common Toxicity Criteria (CTCAE v4). The principal investigator will be responsible for determining the attribution of toxicity as it is related to the investigational drug. All grades of toxicity will be noted and reported appropriately.

### Adverse Event Reporting:

The clinical research coordinator is responsible for collecting and recording all clinical data. As these results are collected, all toxicities and adverse events will be identified and reported to the principal investigator. The principal investigator will determine relationship of the event to the study drug and decide course of action for the study participant. As part of the ongoing monitoring of this study, the PI will maintain an AE summary table to be reviewed during the quarterly audits.

**For Guidelines of Routine Adverse Event Reporting See Appendix 1**

### Study Withdrawal/Discontinuation

This is a low risk imaging protocol; the amount of radioactive peptide is below physiological effects level and the radiation dose is below allowable levels. No adverse events are expected. Adverse events are recorded on the CRF at the following times:

- at the conclusion of the PET/CT scan (approximately 90 min after the injection of the radiopharmaceutical)
- during phone call 18-36 hrs after PET/CT

At any time, subjects may withdraw from the study (i.e., withdraw consent to participate) at their own request. A subject's participation in the study may be discontinued at any time at the discretion of the Investigator and in accordance with his/her clinical judgment. No disadvantage will arise for any subject who withdraws consent for participation at any time or who is withdrawn from the study by the Investigator. Reasons for discontinuation of study treatment will be recorded on the appropriate page of the CRF in any case and may include the following:

- Subject's request for withdrawal
- Investigator's decision that discontinuation is in the best interest of the subject
- Non-compliance with the regimen and timing that might result in dropping out from the study
- Development of an intolerable AE due to study participation as determined by the Investigator, subject, or both.
- Development of an intercurrent illness, condition, or procedural complication, which would interfere with the subject's continued participation.
- 

### Statistical Considerations

This study will evaluate the impact of Ga-DOTATOC PET/CT imaging in the management of patients with neuroendocrine tumors and other somatostatin receptor positive tumors. Participants will be recruited from the Neuroendocrine Tumor Clinics at the University of Iowa Comprehensive Cancer Center Clinics and the University of Iowa Children's Hospital, and individuals may also request to join the study via clinicaltrials.gov. The study will be open-label and subjects with histologically proven neuroendocrine tumor or other somatostatin receptor positive tumors will be recruited. Subjects will

IND # 114,398 for Ga-DOTATOC [name]  
receive Ga-DOTATOC and undergo a PET/CT imaging study. The endpoint of the study will be the change in management of patients based on findings of the Ga-DOTATOC PET/CT scan. Three levels of change will be assessed: no change, minor change and major change based on findings after receiving Ga-DOTATOC and undergoing PET/CT. A previous pilot study of 70 patients (46 of which meet our current inclusion criteria), suggested that 37% of the population had experienced a major change in patient management following Ga-DOTATOC imaging. We operate under the assumption that a 49% major change in management within this population will be clinically relevant should Ga-DOTATOC induce clearer image prompting change.

A sample size of 180 patients achieves 90% power to detect a difference of 12% using a two-sided Z test (also a binomial exact test reaches similar power) when the null hypothesized proportion was used to estimate the standard deviation. The target significance is 0.05 and the actual significance level is 0.045. The results on power justification assume that the proportion of major change in patient management is 37% under the null. Note that we design the power around a two-sided alternative so we can gain more power for the one-sided (as our medical intuition seems to suggest.)

There is a potential for loss to follow-up or attrition within this population. We estimate this rate to be around 10%. In order to have 180 evaluable patients, our estimated sample size is  $180 / (.90) = 200$  subjects.

We will test the null hypothesis of 37% versus a clinically relevant alternative of 49% of major change in patient management. If the null is rejected at significance level of 0.05, we will have enough evidence to attribute our decision to Ga-DOTATOC effect.

Within each category of patient management change (No—Minor—Major), we will report the estimated proportion of subjects as well as 95% confidence intervals around these estimates.

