#### Project Design

This is a prospective, Phase II, single center, open-label study in a total of 200 subjects with histologically proven neuroendocrine tumor or other somatostatin receptor positive tumors. Eligible participants will undergo baseline assessments at enrollment. Study participants will receive  $^{68}\text{Ga}$ -DOTATOC and undergo a PET/CT imaging study. Subjects may receive a second  $^{68}\text{Ga}$ -DOTATOC PET/CT for suspected disease progression, for restaging prior to institution of new therapy, or for measurement of disease response after therapy. This second scan may be obtained at any time from 6-36 months following the first scan.

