**V. MANAGEMENT / THERAPY**

If Ga-DOTATOC PET were not available, your current management strategy would be? (check all that apply)

- Observation (with close follow-up)
- Additional Imaging (CT, MRI) or other non-invasive diagnostic tests
- Tissue Biopsy (surgical, percutaneous, or endoscopic)
- Octreotide LAR
- Surgery for primary tumor / debulking surgery
- Liver directed therapy/Liver transplant
- PRRT
- Chemotherapy or Other Biologic Modifiers (m-TOR inhibitors and/or TK inhibitors)
- Palliative External Beam Radiation Therapy
- Other Supportive care

Signature: \_\_\_\_\_ Date: \_\_\_\_\_ Time: \_\_\_\_\_

**DOTATOC PET-CT Case Evaluation Post-Scan** Patient ID \_\_\_\_\_

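### Rejecting the 37% null cannot be credited to a DOTATOC effect, because 37% is itself the pilot's major-change rate after the same scan

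*Combined protocol and SAP*

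**What the plan says.** Statistical Considerations takes its null from an earlier pilot of 70 patients, 46 of whom meet the current criteria. The pilot "suggested that 37% of the population had experienced a major change in patient management following" 68Ga-DOTATOC imaging. A rate of 49% is set as clinically relevant. The sample size is 180 evaluable patients for a two-sided Z test with 90% power, and the authors add that "we design the power around a two-sided alternative so we can gain more power for the one-sided" case.

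The hypotheses and the rule follow: "We will test the null hypothesis of 37% versus a clinically relevant alternative of 49% of major change in patient management". Then: "If the null is rejected at significance level of 0.05, we will have enough evidence to attribute our decision to" a 68Ga-DOTATOC effect. No direction is attached to the rejection, and no reading is given for non-rejection. For the no, minor and major change categories, "we will report the estimated proportion of subjects as well as 95% confidence intervals around these estimates".

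Project Design describes the study: "This is a prospective, Phase II, single center, open-label study in a total of 200 subjects with histologically proven neuroendocrine tumor". Patients with further tumor types that carry the receptor are admitted as well. All participants receive the scan; no unscanned group is described.

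The Data Analysis section defines the endpoint: "The primary end-point of the study is the change in management of patients based on findings of the" scan. Change is classified by Table 2, which crosses the pre-PET plan with the post-PET plan. The pre-scan form in Appendix II asks what, if the scan "were not available, your current management strategy would be".

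**The concern.** A test against a fixed value can only say how the observed rate stands relative to that value. Here the value was obtained with the same scan, so the test contains no rate without DOTATOC. The rule nevertheless turns rejection into evidence of a DOTATOC effect.

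This is the only stated rule for the primary endpoint, so it will shape the study's conclusion. Rejection would be over-interpreted: a rate above the pilot's could reflect a different case mix or sampling error in the pilot, with the scan doing exactly what it did before. Non-rejection is exposed to the opposite error. A result that repeats the pilot, with more than a third of patients having a major change, fails the test and could be misread as no impact.

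**Working it through.** **Inputs** (all from Statistical Considerations): p0 = 0.37, p1 = 0.49, n = 180, two-sided target alpha 0.05, null variance in the Z statistic, stated power 90%, stated actual alpha 0.045, attrition 10%.

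**1. Reproducing the plan's figures.**
- SE0 = sqrt(0.37 × 0.63 / 180) = 0.03599; SE1 = sqrt(0.49 × 0.51 / 180) = 0.03726.
- Normal-approximation power = Φ((0.12 − 1.96 × 0.03599) / 0.03726) = Φ(1.328) = 0.908.
- Exact binomial power over the rejection region = 0.903.
- Exact two-sided alpha = 0.0445 (lower tail 0.0203, upper tail 0.0241), which rounds to the stated level at two significant figures.
- Enrolment: 180 / 0.90 = 200.

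The design figures stand.

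**2. What the test rejects at n = 180.** With z = (x/180 − 0.37) / 0.03599 and rejection when |z| > 1.96:

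| Major changes | Observed rate | z | Exact 95% CI | Result |
|---|---|---|---|---|
| 53 | 29.4% | −2.100 | 22.9% to 36.7% | rejects, low side |
| 54 | 30.0% | −1.945 | 23.4% to 37.3% | does not reject |
| 67 | 37.2% | 0.062 | 30.1% to 44.7% | does not reject |
| 79 | 43.9% | 1.914 | 36.5% to 51.5% | does not reject |
| 80 | 44.4% | 2.069 | 37.1% to 52.0% | rejects, high side |

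**3. What rejection can mean.** The pilot rate was measured after the scan, and the study rate is measured after the scan. The test compares the two and nothing else. The link from scan to plan comes from the endpoint itself, the pre-PET versus post-PET comparison in Table 2. That link is present at 67/180 just as it is at 80/180, so it cannot depend on crossing 44.4%.

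**4. How firm the benchmark is.** The plan does not give the denominator of the 37%. Assuming 17/46 (37.0%), the 95% Wilson interval is 24.5% to 51.4%; assuming 26/70 (37.1%), it is 26.8% to 48.9%. The 44.4% threshold lies inside both, so a rejection is compatible with the same underlying rate as the pilot's.

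**5. Direction (secondary).** Probability of a low-side rejection, by assumed true rate: 47.2% at 30%, 17.5% at 33%, 6.7% at 35%, 2.0% at 37%. Only the last rate is the plan's own; the others are shown for range. Claiming success only on the high side leaves power at 49% unchanged at 0.903.

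**6. If the evaluable number is not 180.** Over n = 160 to 200, the Z test's exact two-sided error at 37% exceeds 0.05 at 18 of the 41 sizes, reaching 0.056 (for example at n = 199). An exact equal-tailed binomial test stays at or below 0.05 by construction. At n = 180 it has the same cut-offs (53 and 80) and the same power.

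**The case against.** The best defence is that the attribution is built into the endpoint. Change is defined as resulting from the scan findings, and the pre-scan form asks for the plan that would apply without the scan. On that reading, DOTATOC effect is loose wording for scan-prompted change above 37%, and nowhere does the plan claim a contrast with unscanned patients. This is fair as far as it goes. It means the study can support a statement about impact, but through the within-patient change, not through the rejection on which the rule rests it.

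The direction point has a good answer too. The sentence just before the rule names 49% as the alternative, and the sample-size paragraph signals an upward expectation. A reader might infer that the plan means to count a low result as success; the documents do not support that. What remains is a two-sided rule that omits the word upward.

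On non-rejection, the plan never says it means no impact, and the category proportions will be reported with 95% intervals in any case. That meets part of the risk. The rule still leaves the reading open.

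A reader might also infer that the study cannot show impact at all, or that the sample size is wrong. Neither follows: the pre/post forms address impact, and the power calculation reproduces.

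**Conclusion.** The attribution sentence is wrong as written and should be changed. A rejection supports the claim that the major-change rate in this cohort differs from a fixed pilot benchmark of 37%; on the high side, at n = 180, that requires at least 80 major changes (44.4%). It does not support a scan-versus-no-scan claim, and it is not needed for a claim of impact.

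The unstated direction and the missing reading for non-rejection are secondary. The first matters only at 53/180 or fewer, with probability 2.0% if the true rate is 37%. The second matters if the study simply repeats the pilot.

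The central conclusion rests on the text alone: where the 37% comes from, and the absence of a comparator. The counts assume 180 evaluable patients and the Z test as described. Nothing here calls the sample size, power, significance level or forms into question.

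**What to change.** Replace the attribution sentence in Statistical Considerations with:

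> Rejection with an observed proportion above 37% shows that the proportion of patients with a major change in management (Table 2, pre-PET versus post-PET plan) exceeds the fixed pilot benchmark of 37%. It is not a comparison with no scan, and non-rejection does not mean no impact.

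Base the statement of impact on the Table 2 major-change proportion with its 95% confidence interval, which is already planned; at 67/180 the exact interval is about ±7 points ((44.7 − 30.1) / 2 = 7.3).

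Add a note for the case where the final evaluable number is not 180: the approximate Z test's two-sided error can slightly exceed 0.05 (up to 0.056 for 160 to 200 patients). The exact binomial test, which the plan already describes as having similar power, avoids this.

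The cost is wording only. Sample size, planned test, power rationale, forms and data collection stay as they are. The downside is a more modest claim on rejection.
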